2.1.3.5 EuroQoL questionnaire (EQ-5D-3L)

EQ-5D-3L is a standardized health-related quality of life questionnaire developed by the EuroQol Group in order to provide a simple, generic measure of health for clinical and economic appraisal (6). EQ-5D-3L is designed for self-completion by patients.

The EQ-5D essentially consists of 2 pages – the EQ-5D descriptive system and the EQ VAS (See Appendix H). The EQ-5D descriptive system comprises 5 dimensions: mobility, self-care, usual activities, pain/discomfort and anxiety/depression. Each dimension has 3 levels: no problem, some problems, and severe problems.

The 5 dimensional 3-level systems are converted into a single index utility score. Values for the 243 theoretically possible health states defined by the EuroQol classification are calculated using a regression model and weighted according to the social preferences of the UK population (7). The minimum value for the single index utility score is -0.594, which corresponds to a level 3 (severe problems) for mobility, self-care, usual activities, pain/discomfort and anxiety/depression. The maximum value for this index is 1.0, which corresponds to a full health (level 1 (no problem) for mobility, self-care, usual activities, pain/discomfort and anxiety/depression).

The EQ Visual Analogue Scale (VAS) records the respondent's self-rated health on a vertical visual analogue scale. The EQ VAS 'thermometer' has endpoints of 100 (Best imaginable health state) at the top and 0 (Worst imaginable health state) at the bottom. Appendix I provides the SAS code to derive the index utility score using UK based population.

The collection of the EQ-5D-3L will be stopped after the approval of protocol amendment 4. The analyses for the EQ-5D-3L endpoints in LTS12551 study will be restricted to the patients from DRI12544 study and performed to the data observed up to the end of collection.

2.1.3.6 Daily efficacy assessments

On a daily basis before the approval of protocol amendment 4, the patient uses an electronic diary / PEF meter to:

- Measure morning and evening PEF
- Respond to the morning and evening asthma symptom scale questions
- Indicate the number of inhalations / day of salbutamol / albuterol or levosalbutamol / levalbuterol for symptom relief
- Record the number of nocturnal awakenings

The use of the electronic diary/PEF meter will be stopped after the approval of protocol amendment 4. The analyses in LTS12551 study for the above four daily efficacy endpoints in this section will be restricted to the patients from DRI12544 study and performed to the data observed up to the end of collection.

2.1.3.6.1 Peak expiratory flow

At Visit 1, patients are issued an electronic PEF meter to record morning (AM) and evening (PM) PEF, daily salbutamol/albuterol or levosalbutamol/levalbuterol, morning and evening asthma symptom scores, and number of nighttime awakenings due to asthma symptoms that require reliever medications. Patients are instructed on the use of the device, and written instructions on the use of the electronic PEF meter are provided to the patients. In addition, the investigator instructs the patients on how to record the following variables in the electronic PEF meter:

- AM PEF performed within 15 minutes after arising (between 5:30 AM and 10 AM) prior to taking any salbutamol/albuterol or levosalbutamol/levalbuterol
- PM PEF performed in the evening (between 5:30 PM and 10 PM) prior to taking any salbutamol/albuterol or levosalbutamol/levalbuterol
- Patients should try to withhold salbutamol/albuterol or levosalbutamol/levalbuterol for at least 6 hours prior to measuring their PEF
- Three PEF efforts are performed by the patient; all 3 values will be recorded by the electronic PEF meter, and the highest value will be used for evaluation and it is called PEF maximum (MAX). If more than 3 PEF readings are captured, the highest value of 3 readings closest to the Diary start date and time is the PEF MAX. If only 2 PEF readings are captured, the maximum of the 2 PEF readings captured is the PEF MAX. If only 1 PEF readings is captured, the PEF MAX is treated as missing.

Baseline AM/PM PEF is calculated based on the original baseline values from the parent studies. Baseline AM PEF is the mean AM PEF MAX measurements from the 7 morning diaries

(minimum of 4) prior to randomization in parent study, including the morning diary completed on the randomization day prior to the first dose of IMP. Out of the 7 diaries, if less than 4 have missing PEF value, the baseline AM PEF is the mean of the completed AM PEF MAX within the 7 diaries. If 4 or more diaries have missing AM PEF MAX value, the baseline AM PEF is the mean of the 4 AM PEF MAX prior to and closest to randomization during the whole screening period in parent study.

Baseline PM PEF is the mean PM PEF maximum (MAX) measurement from the 7 evening diaries (minimum of 4) prior to randomization in parent study. Out of the 7 diaries, if less than 4 have missing PEF value, the baseline PM PEF is the mean of the completed PM PEF MAX within the 7 diaries. If 4 or more diaries have missing PM PEF MAX value, the baseline PM PEF is the mean of 4 PM PEF MAX prior to and closest to randomization during the whole screening period in parent study.

In addition to the original baselines from parent study, the pre-dose AM/PM PEF at Week 0 of LTS12551 study is to be presented separately, and is calculated in the same way as for the original baseline AM/PM PEF of parent studies.

2.1.3.6.2 Asthma Symptom Score

Patients record overall symptom scores twice a day prior to measuring PEF. The patient's overall asthma symptoms experienced during the waking hours will be recorded in the evening (PM symptom score). Symptoms experienced during the night will be recorded upon arising (AM symptom score). Patients will be instructed to record the severity of symptoms as follows:

AM symptom score:

- 0 = No asthma symptoms, slept through the night,
- 1 = Slept well, but some complaints in the morning. No nighttime awakenings,
- 2 = Woke up once because of asthma (including early awakening),
- 3 = Woke up several times because of asthma (including early awakening),
- 4 = Bad night, awake most of the night because of asthma,

PM symptom score:

- 0 =Very well, no asthma symptoms,
- 1 = One episode of wheezing, cough, or breathlessness,
- 2 = More than one episode of wheezing, cough, or breathlessness without interference of normal activities,

- 3 = Wheezing, cough, or breathlessness most of the day, which interfered to some extent with normal activities,
- 4 = Asthma very bad. Unable to carry out daily activities as usual

The baseline AM/PM symptom score is from the original baselines of parent study, and will be computed following the same algorithm used for baseline AM/PM PEF. An MCID of 0.35 is being used (8).

2.1.3.6.3 Reliever use

The number of salbutamol/albuterol or levosalbutamol/levalbuterol inhalations is recorded daily by the patients in an electronic diary/PEF meter. In the case that Nebulizer solutions are used as an alternative delivery method, the nebulizer dose is converted to number of puffs according to Section 2.1.2.1. Each patient should be reminded that salbutamol/albuterol or levosalbutamol/levalbuterol should be used only as needed for symptoms, not on a regular basis or prophylactically.

A diary day is defined as the period beginning with an Evening diary, and ending with the following day's Morning Diary. The baseline reliever med use is obtained from the original baselines of parent studies, and will be calculated as follows:

The mean of reliever puffs taken in each of the 7 diary days (minimum 4 diary days) prior to randomization, including the diary day that ends with the morning diary completed on the randomization day.

A diary day cannot be included in the calculation if it is not complete, meaning if an evening or morning diary is missing for that diary day. Out of the 7 diary days, if less than 4 are incomplete, the baseline reliever use is the mean of reliever puffs in each of the complete dairy days. If 4 or more diary days are incomplete, the baseline reliever use is the mean of reliever puffs taken in the closest 4 diary days with complete reliever use information prior to randomization.

2.1.3.6.4 Nocturnal awakenings

The number of nocturnal awakening because of asthma symptoms is recorded every morning by the patients in an electronic diary. The baseline number of nocturnal awakenings is obtained from the original baselines of parent studies, and is computed following the same algorithm used for AM PEF.

2.1.3.7 Endpoints linked to the prescribed OCS dose

For the patients from the EFC13691 study only, the following three efficacy endpoints are derived using the prescribed dose of the background oral corticosteroids (OCS) medications. The baseline OCS dose is the original baseline value from the EFC13691 study.

• Percentage change from baseline in the OCS dose

- Proportion of patients achieving a reduction of 50% or greater in the OCS dose compared with the baseline
- Proportion of patients whose background OCS are completely tapered off

2.1.4 Safety endpoints

The primary endpoint of this study is the number (n) and percentage (%) of patients experiencing any treatment-emergent adverse events (TEAE). Adverse Events (AEs), Serious Adverse Events (SAEs), Adverse Events of Special Interest (AESI), adverse events leading to treatment discontinuation are collected at each visit from the time of informed consent signature to the end of study. The safety analysis will be based on the reported adverse events and other safety information, such as clinical laboratory data, vital signs, and ECG.

Observation period

The observation period will be divided into 4 epochs:

- The screening epoch is defined as the time period prior to the date/time of the first dose of IMP in LTS12551.
- The **treatment** epoch is defined as the time period from the date/time of the first dose of IMP to the date/time of the last dose of IMP + 14 days.
- The **follow-up** epoch is defined as the time period from the date/time of the last dose of IMP + 15 days to the end date of 12-week post-treatment follow-up period.
- The **post-study** epoch is defined as the time period from the end date of 12-week post-treatment follow-up period + 1 day.

The **treatment - emergent adverse event period** will include both the **treatment** epoch and **follow-up** epoch. If applicable, the **post-treatment-emergent adverse event period** will be the post-study epoch.

The **pre-treatment adverse event period** will be from starting time of AE reporting up to the first dose of IMP in the LTS12551 study. For all the periods aforementioned, both date and time shall be used in the determination of the periods, as long as they will be available.

2.1.4.1 Adverse events variables

Adverse event observation period

- Pre-treatment adverse events are adverse events that develop or worsen or become serious during the pre-treatment adverse event period.
- Treatment-emergent adverse events are adverse events that develop or worsen or become serious during the treatment-emergent adverse event period.

• Post-treatment-emergent adverse events are adverse events that develop or worsen or become serious during the post-treatment-emergent adverse event period.

All adverse events (including serious adverse events and adverse events of special interest) will be coded to a lower-level term (LLT), preferred term (PT), high-level term (HLT), high-level group term (HLGT), and associated primary system organ class (SOC) using the version of Medical Dictionary for Regulatory Activities (MedDRA) currently in effect at Sanofi at the time of database lock.

The occurrence of all adverse events (regardless of seriousness or relationship to IMP/NIMP) is recorded from the time of signed informed consent for patients from DRI12544 and from the time of the first IMP dose in LTS12551 study for patients from EFC13579, EFC13691 and PDY14192, until the end of the study as defined by the protocol for that patient.

Adverse events of special interest (AESI) and other selected AE groupings will be searched based on the criteria in Table 3

AE Grouping	Criteria
AESI	
Anaphylactic reaction	Anaphylactic reaction algorithmic approach (Introductory Guide for Standardised MedDRA Queries (SMQs) Version 18.1): includes anaphylactic reaction narrow SMQ (20000021) terms; for selection based on occurrence of multiple symptoms, the symptoms must have occurred within 24 hours of each other
Hypersensitivity (medically reviewed)	Hypersensitivity narrow SMQ (20000214) and [AE corrective treatment/therapy='Y' or Action taken with IMP='Drug withdrawn' or Action taken with IMP='Drug interrupted'] followed by medical review (documented process) for selection of relevant systemic hypersensitivity events
Severe injection site reactions that last longer than 24 hours or serious injection site reaction	HLT = 'Injection site reaction' and either with serious status, or with severe status and (AE end date/time –AE start date/time) ≥ 24 hours or ongoing
Severe or serious infection	Primary SOC = 'infections and infestations' and with severe or serious status
Parasitic infection	The Infection Type 'Parasitic' was checked on the eCRF page "Infection Defined as AESI Complementary Form"
Opportunistic infection	The Infection Type 'Opportunistic' was checked on the eCRF page "Infection Defined as AESI Complementary Form"

Table 3 -	Criteria for	r adverse event	s of specia	l interest and	l other selec	ted AE grounings
			s of specia	i multicst and	i other serve	icu All groupings

AE Grouping	Criteria
Drug-related hepatic disorder	Drug-related hepatic disorders - Comprehensive search narrow SMQ (20000006)
Pregnancy	Primary SOC = 'Pregnancy, puerperium and perinatal conditions', or PT in (Aborted pregnancy, False negative pregnancy test, Pregnancy test positive, Pregnancy test urine positive, Ectopic pregnancy termination)
Symptomatic overdose with IMP	The question "Is the event a Symptomatic Overdose with IMP?" is answered "Yes" on the eCRF page "Adverse Event"
Symptomatic overdose with non-IMP	The question "Is the event a Symptomatic Overdose with non-IMP?" is answered "Yes" on the eCRF page "Adverse Event"
Other selected AE grouping	
Injection site reaction	HLT = 'Injection site reaction'
Malignancy	Sub-SMQ (20000091) – Malignant or unspecified tumors
Suicidal behavior	PT in (Completed suicide, Suicidal ideation, Depression suicidal, Suicidal behavior, Suicide attempt)
Partner pregnancy	PT in (Pregnancy of partner, Miscarriage of partner)
Conjunctivitis (narrow)	PT in (Conjunctivitis, Conjunctivitis allergic, Conjunctivitis bacterial, Conjunctivitis viral, Atopic keratoconjunctivitis)
Conjunctivitis (broad)	PT in (Conjunctivitis, Conjunctivitis allergic, Conjunctivitis bacterial, Conjunctivitis viral, Atopic keratoconjunctivitis, Blepharitis, Dry eye, Eye irritation, Eye pruritus, Lacrimation increased, Eye discharge, Foreign body sensation in eyes, Photophobia, Xerophthalmia, Ocular hyperaemia, Conjunctival hyperaemia)
Hypereosinophilia	HLT = 'Eosinophilic disorders' or PT = 'Eosinophil count increased'

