10.4.1.3 Adverse event of special interest

An AESI is an AE (serious or non-serious) of scientific and medical concern specific to the Sponsor's product or program, for which ongoing monitoring and immediate notification by the Investigator to the Sponsor is required. Such events may require further investigation in order to characterize and understand them. AESIs may be added or removed during a study by protocol amendment.

For these AESIs, the Sponsor will be informed immediately (ie, within 24 hours), per SAE notification described in [Section 10.4.3](#), even if not fulfilling a seriousness criterion, using the corresponding pages/screens in the e-CRF.

- Anaphylactic reactions or systemic allergic reactions that are related to IMP and require treatment (see [Appendix H](#) for Definition of Anaphylaxis).
- Severe injection site reactions that last longer than 24 hours.
- Any infection meeting at least one of the following criteria (see [Section 10.6.3](#)):
 - Any serious infection (SAE).
 - Requires parenteral (intravenous, intramuscular, SC) antimicrobial therapy.
 - Requires oral antimicrobial therapy for longer than 2 weeks.
 - Is a parasitic infection.
 - Is an opportunistic infection (see [Appendix I](#)).

Note: Antimicrobial therapy refers to antibiotic, antiviral, and antifungal agents.

- Significant ALT elevation:
 - ALT >5 x the ULN in patients with baseline ALT ≤2 x ULN; or
 - ALT >8 x ULN if baseline ALT >2 x ULN.
- Pregnancy:
 - Pregnancy occurring in a female patient entered in the clinical trial or in a female partner of a male patient entered in the clinical trial. It will be qualified as an SAE only if it fulfills one of the seriousness criteria (see [Section 10.4.1.2](#)).
 - In the event of pregnancy in a female participant, IMP should be discontinued.
 - Follow-up of the pregnancy in a female participant or in a female partner of a male participant is mandatory until the outcome has been determined (see [Section 9.2.1.4.1](#)).

- Symptomatic overdose with IMP/Non-IMP:
 - An accidental or intentional overdose with the IMP/Non-IMP is an event suspected by the Investigator or spontaneously notified by the patient and defined as at least twice the planned dose during an interval of less than 11 days. The circumstances (ie, accidental or intentional) should be clearly specified in the verbatim and symptoms, if any, entered on separate AE forms.

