10.4.5 Guidelines for management of specific laboratory abnormalities

Decision trees for the management of certain laboratory abnormalities by sanofi are provided in [Appendix D](#).

The following laboratory abnormalities should be monitored, documented, and managed according to the related flow chart in protocol appendices:

- Neutropenia;
- Thrombocytopenia;
- Increase in ALT;
- Acute renal insufficiency;
- Suspicion of rhabdomyolysis.

In addition, on treatment eosinophil counts >3000 cells/ μ L (3.0 giga/L) are to be reported as AEs.

NOTE: Increase in ALT is considered as an AESI (see [Section 10.4.1.3](#)).

Appropriate reporting according to categories will appear in the CRF instructions/completion guide.

Table 6 - Summary of adverse event reporting instructions

EVENT CATEGORY	REPORTING TIMEFRAME	SPECIFIC EVENTS IN THIS CATEGORY	CASE REPORT FORM COMPLETION		
			AE form	Safety Complementary Form	Other specific forms
AE (non-SAE, non-AESI)	Routine	Any AE that is not SAE or AESI	Yes	No	No
SAE (non-AESI or AESI)	Expedited (within 24 hours)	Any AE meeting seriousness criterion per Section 10.4.1.2	Yes	Yes	No
Adverse Event of Special Interest	Expedited (within 24 hours)	As per Section 10.4.1.3	Yes	Yes	No

Abbreviations: AE = Adverse event; AESI = Adverse event of special interest; SAE = Serious adverse event

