2	23-Nov-2016	Protocol amendment 4 reduces the frequency of assessments for the ACQ-5, AQLQ, clinical laboratories, ECG and ADA variables for all patients in the LTS12551 study.	The scheduled visits and corresponding analysis windows for the endpoints of ACQ-5, AQLQ, clinical laboratories, ECG and ADA are adjusted accordingly per the reduced scheduled visits in the protocol amendment 4.
2	23-Nov-2016	The patient population from study EFC13691 is expected to be different from the	All the planned analyses in LTS12551 study will be performed and presented separately for the

Statistical Analysis Plan SAR231893-LTS12551 - dupilumab

SAP	Data		
number	approved	Rationale	Description of statistical changes
		patient population from the DRI12544, EFC13579 or PDY14192 studies. The patients from EFC13691 are more severe at the baseline of the parent study and are using a different background controller medication, and thus potentially have different safety profiles in general from the patient population from the other parent studies.	patients from EFC13691 study and the patients from DRI12544, EFC13579 or PDY14192 studies, except for the endpoints that are particularly collected for the patients from EFC13691 study only.
3	This version	The layouts of all outputs are changed to avoid potential confounding introduced by between-study variation.	The treatment category (Naïve, Re- treated, Interrupted treatment, and Continuously treated) is removed.
			The layouts of all outputs are changed to:
			For the patients from EFC13691 study, results of each planned analysis will be presented by "Placebo/Dupilumab, Dupilumab/Dupilumab, and All" (see Section 2.3.2).
			For the patients from DRI12544/EFC13579/PDY14192 studies, results of each planned analysis will be presented by the parent study and "All", and by "Placebo/Dupilumab and Dupilumab/Dupilumab" within each parent study (see Section 2.3.2).
3	This version	To be consistent with ISS SAP	The definition of AESI and other selected AE groupings are updated in Section 2.1.4.1

Property of the Sanofi Group - strictly confidential

Page 15

SAP version	Date		
number	approved	Rationale	Description of statistical changes
3	This version	To be consistent with ISS SAP by including the combined PCSA criteria for adult and adolescents	PCSA criteria in Appendix A are updated

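### SAP Table 3 has no rule for two of the protocol's five infection AESI criteria, so non-severe infections that qualify only through antimicrobial therapy are missing from the AESI outputs; the SAP also labels every overdose serious

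*SAP*

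**What the plan says.** **Infections.** Protocol 10.4.1.3 counts as an AESI "Any infection meeting at least one of the following criteria". The five criteria are a serious infection, "Requires parenteral (intravenous, intramuscular, SC) antimicrobial therapy", "Requires oral antimicrobial therapy for longer than 2 weeks", a parasitic infection and an opportunistic infection. All must be reported within 24 hours.

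SAP 2.1.4.1 says AESIs are found by the criteria in Table 3, and SAP 2.4.5.1 builds the AESI summaries on those criteria. Table 3 has three infection rows. The first is "Primary SOC = 'infections and infestations' and with severe or serious status". The other two use the infection type, parasitic or opportunistic, ticked on the "Infection Defined as AESI Complementary Form".

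**Who sets the definition.** Protocol 11.4.3.1.2 leaves AESI definitions and the search method to the SAP. Protocol 10.4.1.3 names protocol amendment as the way to add or remove an AESI. SAP 1.6 records for version 3, citing consistency with the ISS SAP: "The definition of AESI and other selected AE groupings are updated in Section 2.1.4.1". It does not itemise what changed.

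**Overdose.** SAP 2.4.3.2 classes cases of overdose as serious adverse events and lists them so. Overdose is not among the seriousness criteria in protocol 10.4.1.2. Protocol 10.4.1.3 and SAP Table 3 both make symptomatic overdose an AESI. Protocol Table 5 puts asymptomatic overdose under routine reporting.

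**ALT.** The first limb of the protocol's ALT AESI is "ALT >5 x the ULN in patients with baseline ALT ≤2 x ULN; or". The second limb is more than 8 x ULN when baseline exceeds 2 x ULN. SAP 2.4.5.1 mentions AESIs identified from laboratory values and gives ALT elevation as its example. The only liver row in Table 3 is a MedDRA query.

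**The concern.** Long-term safety is the primary objective, and protocol 10.6.3 treats infection as a specific risk. Sites must expedite some infections as AESIs that the analysis, read literally, does not count as AESIs. Someone reading the study report would take its infection AESI rates to be those of the protocol definition. For one subset they would not be.

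The overdose sentence works the other way: a listing would call events serious that the protocol does not. The ALT phrase leaves a programmer to invent a rule for a table the SAP announces.

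**Working it through.** The plan states no figure on this point, so the check is a comparison of definitions.

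**1. Infection criteria against Table 3**

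| Protocol 10.4.1.3 criterion | Table 3 rule |
|---|---|
| Serious | Yes (row also admits severe) |
| Parenteral antimicrobial | None |
| Oral antimicrobial > 2 weeks | None |
| Parasitic | Yes (form tick) |
| Opportunistic | Yes (form tick) |

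Criteria without a rule: 5 − 3 = 2.

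**2. Which infections are lost**

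- An infection can meet any non-empty combination of the five criteria: 2^5 − 1 = 31.
- Combinations using only the three covered criteria: 2^3 − 1 = 7.
- Combinations with at least one treatment criterion: 31 − 7 = 24.
- Of those 24, the ones with no covered criterion number 2^2 − 1 = 3: parenteral alone, oral > 2 weeks alone, or both.
- If the event is graded severe, the first row catches all 24 and none is missed. If it is not severe, 3 of 24 are missed.

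These are counts of patterns, not of patients or events.

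**3. Outputs affected.** In SAP 2.4.5.1 these are AESI incidence, the overview within each AESI, the Kaplan-Meier plot and cumulative incidence, and events per 100 patient-years. The AESI subgroup tables in SAP 2.4.5.6 are also affected. The all-TEAE tables do not depend on Table 3, so the same events appear there and in the primary endpoint.

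**4. ALT.** The Appendix A cut-offs are > 3, > 5, > 10 and > 20 ULN.

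- Protocol AESI set: {baseline ≤ 2x, peak > 5x} or {baseline > 2x, peak > 8x}.
- Both parts lie within peak > 5x, so the > 5 ULN row misses 0.
- With baseline known, that row adds only patients with baseline > 2x and peak > 5x to ≤ 8x.
- The listing in SAP 2.4.5.3 shows baseline and the full profile, so it separates the two groups.

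**5. ALT baseline.** SAP 2.4.5 and 2.4.5.3 use the parent-study baseline, and SAP 2.5.3 groups a missing baseline with normal. The ALT note in protocol Appendix D uses the baseline visit or, failing that, the latest earlier ALT. The flow-chart footnotes take Day 1 baseline data for rollover patients from the parent study's end-of-treatment visit. The choice can matter. Take a parent-study baseline of 1x, a Day 1 value of 2.5x and a peak of 6x ULN:

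- Parent-study baseline: 1 ≤ 2 and 6 > 5, so an AESI.
- Day 1 value: 2.5 > 2 and 6 ≤ 8, so not an AESI.

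**The case against.** The best defence is that the difference is authorised. The protocol hands AESI definitions to the SAP, its own list serves rapid notification rather than tabulation, and SAP 1.6 logs the change with a reason. This shows that the update as a whole was deliberate. It does not show that these two criteria were meant to go: the log names none as dropped, the current protocol keeps all five, and it gives amendment as the route for removal. A breach cannot be asserted, but the mismatch remains.

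The loss is also narrow. A reader might infer that every infection treated parenterally or with long oral courses disappears. The documents do not support that, because any such infection that is also serious, severe, parasitic or opportunistic is still counted. Table 3 is in fact wider than the protocol in admitting severe infections. The protocol also promises patient listings of all AEs, TEAEs and AESIs, so individual cases remain visible.

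On ALT, a reader might infer that cases are lost. They are not. Protocol 10.4.2 has AESI-level abnormalities recorded as AEs, and the > 5 ULN row and the patient listing contain these patients. Whether the MedDRA query would find them cannot be judged from the documents.

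On overdose, a reader might infer inflated SAE tables. Nothing in SAP 2.4.5.1 says those tables are rebuilt from the compliance section; what is affected is the listing that section describes.

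**Conclusion.** The point holds in a limited form and should be corrected. Two of five infection criteria have no search rule. Infections that are AESIs only through antimicrobial therapy, and are not severe, are left out of the AESI outputs. General TEAE reporting and the primary endpoint are intact. No patient or event count can be given, because the documents contain no infection or treatment rates.

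The overdose wording is a direct contradiction between SAP 2.4.3.2 on one side and the protocol and Table 3 on the other, confined to how cases are listed. The ALT point is minor: a rule is referred to but not defined, with no data lost.

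This rests on Table 3 being applied as written, and on serious infections coding to the infections system organ class, so that the first row catches them.

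**What to change.** 1. **Infections.** Add a Table 3 row for protocol-defined infection AESIs, identified by a completed "Infection Defined as AESI Complementary Form", and keep the ISS groupings as additional rows. First check that the form is completed for all five criteria. Protocol Table 6 requires a "Safety Complementary Form" for every AESI but does not name the infection form. If the two criteria were dropped on purpose, say so in SAP 1.6 and reconcile that with protocol 10.4.1.3.
2. **Overdose.** Reconcile SAP 2.4.3.2 with protocol 10.4.1.2, 10.4.1.3 and Table 5, so that an overdose is listed as an SAE only when a protocol seriousness criterion is met.
3. **ALT.** Either add a row with the protocol thresholds or remove the ALT phrase from SAP 2.4.5.1. A new row must state which baseline applies and how a missing one is handled, after SAP 2.4.5, 2.4.5.3 and 2.5.3 are reconciled with protocol Appendix D.

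The cost is one or two table rows and one or two reworded sentences. Table 3 already reads the infection form for two rows, so item 1 should need no new data if the form check succeeds. Medication records would be a weaker fallback: SAP 2.5.3 bars imputing medication dates, and the documents show neither a recorded route nor a link from a medication to an event. ALT values are already collected.
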